3.6 Post Study Drug Study Follow up

In this study, major adverse cardiovascular events (MACE) and the Day 28 MRI is a key endpoint of the study. Post treatment follow-up is of critical importance and is essential to preserving subject safety and the integrity of the study. Subjects who discontinue study drug must continue to be followed for collection of outcome and/or survival follow-up data as required and in line with Section 5 until death or the conclusion of the study.

3.6.1 Withdrawal of Consent

Subjects who request to discontinue study drug will remain in the study and must continue to be followed for protocol specified follow-up procedures. The only exception to this is when a subject specifically withdraws consent for any further contact with him/her or persons previously authorized by subject to provide this information. Subjects should notify the investigator of the decision to withdraw consent from future follow-up **in writing**, whenever possible. The withdrawal of consent should be explained in detail in the medical records by the investigator, as to whether the withdrawal is from further treatment with study drug only or also from study procedures and/or post treatment study follow-up, and entered on the appropriate CRF page. In the event that vital status (whether the subject is alive or dead) is being measured, publicly available information should be used to determine vital status only as appropriately directed in accordance with local law.

3.6.2 Lost to Follow-Up

All reasonable efforts must be made to locate subjects to determine and report their ongoing status. This includes follow-up with persons authorized by the subject as noted above. Lost to follow-up is defined by the inability to reach the subject after a minimum of three documented phone calls, faxes, or emails as well as lack of response by subject to one registered mail letter. All attempts should be documented in the subject's medical records. If it is determined that the subject has died, the site will use permissible local methods to obtain the date and cause of death.

If investigator's use of third-party representative to assist in the follow-up portion of the study has been included in the subject's informed consent, then the investigator may use a Sponsor-retained third-party representative to assist site staff with obtaining subject's contact information or other public vital status data necessary to complete the follow-up portion of the study. The site staff and representative will consult publicly available sources, such as public health registries and databases, in order to obtain updated contact information. If after all attempts, the subject remains lost to follow-up, then the last known alive date as determined by the investigator should be reported and documented in the subject's medical records.

4 STUDY DRUG

Study drug includes both Investigational [Medicinal] Product (IP/IMP) and Non-investigational [Medicinal] Product (Non-IP/Non-IMP) and can consist of the following:

Table 4-1: Study Drugs for CV006004: Parts 1 and 2

Product Description / Class and Dosage Form	Potency	IP / Non-IMP	Blinded or Open Label	Packaging/ Appearance	Storage Conditions (per label)
BMS-986141-01 Tablet	0.8mg	IP	Blinded	Plain, white to pale-yellow, oval tablet	Store at 2-8°C; In a tightly closed container; light and moisture protected
BMS-986141-01 Tablet	4mg	IP	Blinded	Plain, white to pale-yellow, oval tablet	Store at 2-8°C; In a tightly closed container; light and moisture protected
BMS-986141-01 Tablet	Placebo for 0.8 mg and 4 mg	IP	Blinded	Plain, white to pale-yellow, oval tablet	Store at 2-8°C; In a tightly closed container; light and moisture protected
Acetylsalicylic acid (ASA)	As available locally such that dose is 75-162 mg	Non-IP	Open	Commercially Sourced (Not Provided by BMS)	Per manufacturer's instructions.

4.1 Investigational Product

An investigational product, also known as investigational medicinal product in some regions, is defined a pharmaceutical form of an active substance or placebo being tested or used as a reference in a clinical study, including products already with a marketing authorization but used or assembled (formulated or packaged) differently than the authorized form, or used for an unauthorized indication, or when used to gain further information about the authorized form.

The investigational product should be stored in a secure area according to local regulations. It is the responsibility of the investigator to ensure that investigational product is only dispensed to study subjects. The investigational product must be dispensed only from official study sites by authorized personnel according to local regulations.

4.2 Non-investigational Product

Other medications used as support or escape medication for preventative, diagnostic, or therapeutic reasons, as components of the standard of care for a given diagnosis, may be considered as non-investigational products.

In this protocol, non-investigational product(s) are: Acetylsalicylic acid (ASA).

The Sponsor will not be providing the ASA. It should be sourced locally by the investigator in commercial packaging.

4.3 Storage of Study Drug

The product storage manager should ensure that the study drug is stored in accordance with the environmental conditions (temperature, light, and humidity) as determined by BMS. If concerns regarding the quality or appearance of the study drug arise, the study drug should not be dispensed and contact BMS immediately.

Study drug not supplied by BMS will be stored in accordance with the package insert.

Please refer to [Section 9.2.2](#) for guidance on IP records and documentation.

The blinded study medication requires refrigeration and protection from light and moisture. While at the study site the blinded study medication must be maintained at a temperature between 2-8°C.

Subjects will be instructed to ensure study medication is kept refrigerated between 2-8°C and protected from light and moisture while in their possession. Refer to [Table 4-1](#) for the specific storage requirements for the blinded study medication.

4.4 Method of Assigning Subject Identification

At the screening visit each subject will be assigned a unique sequential subject number by the Interactive Voice Response System (IVRS). The subject number will consist of 5 digits which are assigned sequentially (00001, 00002, 00003, etc.) by the IVRS. This number will be used for identification throughout the study and will not be used for any other participant. Screening of subjects with lacunar infarcts will be capped at approximately 20%.

Randomization schedules will be generated by BMS and kept by the IVRS vendor. Subjects will be randomly assigned to 1 of the 4 blinded treatment groups (BMS-986141 0.8 mg, BMS-986141 4.8 mg, BMS-986141 8 mg, or placebo) by the IVRS. Randomization will be limited to the two lower doses of BMS-986141 or placebo in a 1:1:1 ratio until after DMC review of safety and laboratory data from the Day 28 study visit for at least 10% of the planned total subjects. If the DMC recommends proceeding to inclusion of the highest dose, subsequent randomization will be in a 1:1:1:1 ratio.

At all study visits when study drug is dispensed, each subject will be assigned a container number by the IVRS. Container numbers will be assigned non-sequentially and will correspond to the numbers printed on the packages and bottles containing study drug, and will be recorded on the appropriate eCRF. The IVRS will be available 24 hours per day, 7 days a week.

4.5 Selection and Timing of Dose for Each Subject

Study drug may be administered in the clinical facility or self-administered by the subject or their caregiver at home. Caregivers will need to be properly instructed about study medication dosing requirements by the study staff. The same caregiver should assist the subject with their daily dosing.

Double blind study medication (BMS-986141 or matching placebo) will be taken once daily. The first dose of study medication should be taken as soon as possible after randomization. Subsequent doses including on Day 2 of the study should be taken in the morning and before breakfast. The subject must be in a fasted state for at least two (2) hours when taking study medication. Subjects should wait at least one (1) hour before consuming food.

Initially, each daily dose of double blind study medication will consist of 4 tablets. The double blind treatment period will be 28 days for Part 1 of the study and 90 days for Part 2 of the study. Drug supplies that may become available in early 2017 may allow for dosing with 2 tablets per day. Sites will be provided with instructions and guidance on how to implement this change if it is to occur.

Subjects treated in Part 1 of the study MUST be instructed to stop study medication dosing on Day 28, even if visit will not occur on exactly Day 28.

Sparse PK sampling will occur at the Day 28 visit. Subjects will be instructed not to take their study medication dosage on Day 28 prior to coming to the study site.

Additional drug, dosage and mode of administration

All subjects will be dispensed open label ASA at a dose prescribed by the investigator (not less than 75 mg and not to exceed 162 mg per day). It is recommended subjects remain on the same dose of ASA throughout the treatment period.

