A study visit will be performed on the day of hospital discharge. Subjects will be instructed to report any adverse events occurring after hospital discharge, including any occurrence of bleeding or signs or symptoms of recurrent stroke.

The study site will contact the subject by telephone on Day 10 \pm 3 days to assess study medication compliance and assess the subject's health status.

A study visit will be performed 28 \pm 3 days after the first dose of study medication. Head MRI will be performed for assessment of unrecognized brain infarctions. For subjects enrolled in Part 1 of the study, Day 28 will be the end of the treatment period and it is preferred that the study visit be performed on Day 28 or earlier.

Part 2 of the study will only be initiated after regulatory review of 90-day preclinical toxicology study reports and the updated Investigator Brochure. For subjects enrolled in Part 2 of the study, the treatment period will be 90 days. There will be no change in study visits through Day 28. Additional treatment period study visits for these subjects will occur 56 and 90 days after the beginning of the treatment period.

Pharmacokinetic (PK) sampling will be performed in all subjects. See [Section 5.5](#).

A sub-study conducted at select sites will enroll approximately 50 subjects per arm for which additional blood will be collected for analysis of platelet aggregation as a pharmacodynamic biomarker. See [Section 5.6](#).

Follow-Up Period

The follow-up period will last until the later of 90 days after the first dose of study drug or 30 days after treatment discontinuation. Subjects will be instructed to report any adverse events that occur during the follow-up period. No additional study assessments are planned at the follow-up visit, which may be an in-person study visit or if necessary conducted by telephone.

Duration of Study

The expected duration of the study, from first subject, first visit through the last subject, last follow-up visit (eg, the End of the study), is approximately 28 months.

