Central Laboratory						Chemistry and hematology samples for Day 1 pre-dose labs and those drawn throughout the study to be analyzed by the central laboratory. Urinalysis testing (refer to Table 5.3.7-1) will be done locally for all time points.
Pregnancy test (serum or urine) WOCBP only	X			X		To be done locally. All WOCBP must have a negative pregnancy test within 24 hours prior to dosing.
Clinical Chemistry	X	X ^c		X		
Hematology	X	X ^c		X		

Table 5.1-2: Part 1 Procedural Outline (CV006004)

Procedure	Day 1 (Visit 2)	Day of Hospital Discharge ^a (Visit 3)	Day 10 Telephone Contact ^b (Visit 4)	Day 28 (EOT) / Early D/C ^{a,b} (Visit 5)	Follow-up Day 90 ^{a,b} (Visit 6)	Notes
Urinalysis	X	X		X		To be analyzed locally at all time points
MRI	X*			X**		*No later than 24 hours after randomization if not done prior to randomization ** +/- 3 days from Day 28 For subjects that stop treatment early the MRI should be done on Day 28
Pharmacokinetic (PK)						
Serial/Sparse Blood PK Sampling	X			X		On Day 1, the last PK sample is collected 24 hrs (+/- 11 hrs) after first dose of study medication and before Day 2 dose
Biomarker Assessments						
Platelet Aggregation	X			X		To be performed at select sites. Samples should be collected at the same time as the time-matched PK samples. Day 1-24 hr sample to be collected 24 hrs (+/- 11 hrs) after first dose of study medication and before Day 2 dose.
Exploratory Biomarker Assessments						
[REDACTED]	■			■		[REDACTED]
[REDACTED]	■			■		[REDACTED]

Table 5.1-2: Part 1 Procedural Outline (CV006004)

Procedure	Day 1 (Visit 2)	Day of Hospital Discharge ^a (Visit 3)	Day 10 Telephone Contact ^b (Visit 4)	Day 28 (EOT) / Early D/C ^{a,b} (Visit 5)	Follow-up Day 90 ^{a,b} (Visit 6)	Notes
						
Clinical Drug Supplies						
Randomize	X					
Review study drug administration compliance (BMS- 986141 or matching placebo with ASA)		X	X	X		Subjects MUST be instructed to stop study medication dosing on Day 28, even if visit will not occur on Day 28. Telephone contact with subject to review medication compliance and assess subject's health status
Dispense Study Drug	X					

^a Subjects should participate in all study visits even if study medication dosing has been discontinued.

^b Visit window is +/- 3 days.

^c Laboratory tests may be done on the day prior to discharge.

Table 5.1-3: Part 2 Procedural Outline (CV006004)

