8.4.4 Pharmacokinetic Analyses

Pharmacokinetics of BMS-986141 and BMT-162856 will be explored.

A population pharmacokinetic model will be developed to understand the pharmacokinetics of BMS-986141. The potential effect of covariates (eg, body weight, age, gender, race, renal function, liver function, co-administration of other medicine) on the pharmacokinetics of BMS-986141 will be also explored. These results will be reported separately.

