11 LIST OF ABBREVIATIONS

Term	Definition
ABCD2	neurological assessment scores (age, blood pressure, clinical features, duration, diabetes)
ACS	acute coronary syndrome
AE	adverse event
AF	atrial fibrillation
ALT	alanine aminotransferase
aPTT	activated partial thromboplastin time
ASA	acetylsalicylic acid
AST	aspartate aminotransferase
AT	aminotransaminases
AUC	area under the concentration-time curve
AUC(0-24)	area under the concentration-time curve from time zero to 24 hours post dose
BMI	body mass index
BMS	Bristol-Myers Squibb
BP	blood pressure
BT	bleeding time
BUN	blood urea nitrogen
C	Celsius
C(24)	concentration at 24 hours
CEC	Clinical Events Adjudication Committee
CFR	Code of Federal Regulations
CI	confidence interval
CK	creatin kinase
CK-MB	creatin kinase- myocardial fraction
cm	Centimeter
Cmax, CMAX	maximum observed concentration
COX-2	cyclooxygenase-2
CRF	Case Report Form, paper or electronic
CRNM	Clinically Relevant Non-Major

Term	Definition
CSF	cerebrospinal fluid
CT	computerized tomography
Ctrough	Trough observed plasma concentration
CV	cardiovascular
CYP	cytochrome P450
D-dimer	fibrin degradation product
D/C	Discontinue
DDI	drug-drug interaction
DILI	drug induced liver injury
dL	Deciliter
DMC	Data Monitoring Committee
DWI	Diffusion-weighted imaging MRI
ECG	electrocardiogram
eCRF	Electronic Case Report Form
EDC	Electronic Data Capture
EDTA	ethylenediaminetetraacetic acid
eg	exempli gratia (for example)
E _{max}	Asymptotic maximum change from placebo effect
EOT	end of treatment
ESR	Expedited Safety Report
F1.2	F1.2 fragment of prothrombin
FDA	Food and Drug Administration
FLAIR	fluid-attenuated inversion recovery
FSH	follicle stimulating hormone
g	gram
GCP	Good Clinical Practice
GPIIb/IIIa	glycoprotein IIb/IIIa
h	hour
Hb	hemoglobin
HBsAg	hepatitis B surface antigen
HBV, HepB	hepatitis B virus

Term	Definition
HCG	human chorionic gonadotropin
HCV, HepC	hepatitis C virus
HepA	hepatitis A virus
HIPAA	Health Insurance Portability and Accountability Act
hr, hrs	hour, hours
HR	heart rate
HRT	hormone replacement therapy
IAC	Imaging Adjudication Committee
IB	Investigator Brochure
ICD	International Classification of Diseases
ICF	informed consent form
ICH	International Conference on Harmonisation
ie	id est (that is)
IEC	Independent Ethics Committee
IMP	investigational medicinal products
IND	Investigational New Drug Exemption
INR	international normalized ratio
IP	investigational product
IRB	Institutional Review Board
IST	International stroke trial

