32. Section 7.1, Data Monitoring Committee: added 2nd paragraph describing that the DMC will review the safety data from the at least 10% of the total planned subjects randomized to the 0.8, 4.8 or placebo groups and will make their recommendation before randomizations to the 8 mg treatment arm can begin.
33. Section 8.1, Sample Size Determination
 - a) 1st paragraph, 3rd sentence: changed 16 mg dose to 8 mg
 - b) Updated 2nd paragraph to describe randomizations ratios and sample size calculations based on the possible staggered randomization from 3 treatment groups to 4 treatment groups.
 - c) Added Table 8.1-1: Randomization Targets
34. Section 8.3.3 Exploratory Endpoint(s):
 - a) 2nd bullet: Deleted NR-2 peptide
 - b) Added 3rd bullet to state change from baseline on renal biomarkers is a new exploratory endpoint
 - c) former 3rd bullet, now 4th bullet: added that polymorphisms in genes related to platelet activity will also be studied.
35. Section 8.4.1 Demographics and Baseline Characteristics
 - a) 2nd paragraph: deleted summaries of baseline variable by study phase
 - b) added 3rd paragraph stating separate summaries taking into account the length of treatment and randomization phase will be provided.
36. Section 8.4.2.1, Primary Efficacy Endpoint Analysis:
 - a) 1st paragraph, 4th sentence: updated the dose levels to reflect change from 16 mg to 8 mg treatment arm.
 - b) 3rd paragraph: deleted.
 - c) new 3rd paragraph added to address new covariate.
37. Section 8.4.3, Safety Analyses:
 - a) Added new 1st paragraph describing that for safety analyses separate summaries taking into account length of treatment and randomization phase will be provided.
 - b) 1st paragraph (now 2nd paragraph): added a 3rd sentence stating that a single variable based on study change points (length of treatment and randomization phase) will be included as a stratum in the calculation of the CIs.
 - c) 2nd paragraph (now 3rd paragraph): delete 4th sentence stating AE summaries will be presented by treatment length.

38. Section 8.4.4, Pharmacokinetic Analyses, 1st paragraph: deleted reporting of C_{max}, AUC(0-24), C(24) after first dose, and C(24) on Day 28 due to the need to expand PK sample collection windows.

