7.7 Pharmacokinetic Analyses

Analyses of pharmacokinetics will be conducted on the Pharmacokinetic Population. Pharmacokinetics of BMS-986141 and BMT-162856 will be summarized with descriptive statistics for Cmax, AUC(0-24), C(24) after first dose, and C(24) on Day 28.

As well, a population pharmacokinetic model will be developed to understand the pharmacokinetics of BMS-986141. The potential effect of covariates such as body weight, age, gender, race, renal function, liver function, and co-administration of other medicines on the pharmacokinetics of BMS-986141 will be explored in this analysis. Details of this analysis and its results will be reported in a separate document.

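### Protocol 4.5 ties the PK dose hold and the Part 1 dosing stop to Day 28 rather than to the visit, and SAP 7.7 keeps a Day 28 C(24) summary with no visible rule on which samples qualify

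*Protocol*

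**What the plan says.** **Dosing instructions.** Protocol 4.5 places the sparse PK samples at the Day 28 visit and gives two instructions by study day. Part 1 subjects "MUST be instructed to stop study medication dosing on Day 28, even if visit will not occur on exactly Day 28". For the PK draw, "Subjects will be instructed not to take their study medication dosage on Day 28 prior to coming to the study site".

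**Visit timing.** Tables 5.1-2 and 5.1-3 both carry the footnote "Visit window is +/- 3 days" for this visit. For Part 1, Protocol 3.1 adds that "it is preferred that the study visit be performed on Day 28 or earlier". Table 5.5-1 asks for a sample before the Day 28 dose and another 3 hours after it (± 1 hour). It sets no interval since the previous dose.

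**PK analysis.** Current Protocol 8.4.4 says only "Pharmacokinetics of BMS-986141 and BMT-162856 will be explored", followed by a population PK model. SAP 7.7 says the same two analytes "will be summarized with descriptive statistics for Cmax, AUC(0-24), C(24) after first dose, and C(24) on Day 28". The protocol's abbreviation list gives C(24) as "concentration at 24 hours".

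**Rules on which samples count.** The day ranges in SAP 8.3 cover laboratory, ECG and vital-sign data. SAP 8.2 covers values below the quantification limit. The evaluable PK subset in SAP 6.3 depends on the Day 1 profile only. SAP 8 refers to a sponsor standard for time windowing, and SAP 9 allows PK to be reported separately. Neither of those sources is in the documents.

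**The concern.** A trough is defined by the time since the last dose, but both instructions are anchored to a study day that need not be the day of the draw. The protocol foresees off-day visits, since the stop instruction mentions them, yet it does not move the hold to the visit.

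Two kinds of sample could then enter a Day 28 C(24) table wrongly. In Part 1, a visit on Day 30 or 31 comes two or three days after the last dose, so its value is too low. At a visit away from Day 28 while dosing continues (Days 25-27 in Part 1, any off-day in Part 2), nothing in Protocol 4.5 tells the subject to hold that morning's tablets, so a value could be too high. A Part 1 visit on Days 29-31 also has no dose for its 3-hour sample to follow.

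What is at stake is the accuracy of a descriptive exposure table, and agreement between the protocol and the SAP on whether that table should exist.

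**Working it through.** The plan states no figure to reproduce here. The check is a timeline and a decay calculation.

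**Inputs**
- Visit window ± 3 days (Tables 5.1-2 and 5.1-3).
- Mean terminal half-life T = 35.2-45.5 h, and accumulation index R = 1.3-1.9 (Protocol 1.4.1.1).
- Planned randomisation before the 8 mg arm opens: 44 + 33 = 77 in each of the 0.8 mg and 4.8 mg arms, out of 347 per arm (SAP Table 5-1, where the counts are described as estimates).
- No Part 1 subject is randomised after the 8 mg arm opens (SAP 2.2).
- Assumptions: once-daily morning dosing, visits at the usual dosing time, single-exponential decline.

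**Step 1, window.** 28 - 3 = 25 and 28 + 3 = 31, so Days 25-31.

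**Step 2, Part 1 visits after Day 28, with the Day 28 dose taken.** Ratio to the 24 h value = 0.5^((t - 24)/T).

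| Visit | Hours since last dose | Ratio, T = 35.2 h | Ratio, T = 45.5 h |
|---|---|---|---|
| Day 29 | 24 | 1 | 1 |
| Day 30 | 48 | 0.5^(24/35.2) = 0.623 | 0.5^(24/45.5) = 0.694 |
| Day 31 | 72 | 0.5^(48/35.2) = 0.389 | 0.5^(48/45.5) = 0.481 |

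**Step 3, off-day visit with the morning dose already taken.** A sample 3 h after a home dose, against the 24 h value, is 2^(21/T): 2^(21/35.2) = 1.51 and 2^(21/45.5) = 1.38. This error runs the opposite way to Step 2.

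**Step 4, share of each arm that can be affected by Step 2.** Part 1 lies wholly within the period before the 8 mg arm opens, so it is at most 77/347 = 22.2% of each lower-dose arm as planned, and none of the 8 mg arm.

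**Step 5, effect on a pooled mean.** The documents do not give the proportion of late visits. Assume 10% of Part 1 subjects are seen on Days 30-31: 0.10 × 22.2% = 2.22% of the arm.
- All at 48 h, longer half-life: 2.22% × (1 - 0.694) = 0.7%.
- All at 72 h, shorter half-life: 2.22% × (1 - 0.389) = 1.4%.

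**Step 6, sensitivity.** Reading the accumulation index as an effective half-life, the fraction left after 24 h is 1 - 1/R: 0.231 for R = 1.3 and 0.474 for R = 1.9. Over 48 h it is 0.053 and 0.224. Under the same 10% assumption the largest fall is 2.22% × (1 - 0.053) = 2.1%.

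**Step 7, protocol against SAP.** SAP 2.4 describes the July 2016 amendment, so the SAP was written after it. Current Protocol 8.4.4 has no Cmax, AUC(0-24) or C(24) summary; current SAP 7.7 has all of them. Item 38 of the Amendment 06 change list is context only. It shows the removal was deliberate, covering Cmax, AUC(0-24), C(24) after the first dose and "C(24) on Day 28 due to the need to expand PK sample collection windows".

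**The case against.** **The hold sentence, read naturally, already means the visit morning.** It follows directly on the statement that PK is drawn at the Day 28 visit, and it speaks of coming to the site. Table 5.5-1 also requires a pre-dose sample. This has force. It defeats a harsher reading that a reader might infer: that a Part 1 subject seen on Day 31 skips the Day 28 dose, so that the sample is 96 h old at 24-33% of the trough. Nothing in the protocol sensibly asks for that, so I do not rely on it. But a text that needs this reading should say so, and it cannot change the Part 1 stop, which is explicit.

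**Late visits should be few.** Protocol 3.1 prefers Part 1 visits by Day 28, and a Day 29 visit gives a valid trough. Both are true. The preference is not a requirement, however, and it steers Part 1 visits towards days that have no written hold.

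**There is no real conflict between the documents.** Exploring PK does not forbid a descriptive C(24). The windows that Amendment 06 widened were those for Day 1 samples (change list, item 27), so the log does not establish the Day 28 timing problem. That stands: the timing problem rests on Protocol 4.5 and the visit window. It remains that SAP 7.7 keeps four summaries absent from the current protocol and does not flag the difference.

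**A rule may exist elsewhere.** The sponsor's windowing standard or a separate PK report could screen the samples, and a 48 h value is not C(24) by its own abbreviation. This is possible, so the claim is limited to the visible text.

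**Conclusion.** The point holds as a minor one. The protocol anchors the dose hold and the Part 1 stop to Day 28 rather than to the visit. The SAP retains a Day 28 C(24) summary that the current protocol lacks, with no visible limit on which samples count.

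The consequence is confined to descriptive PK. Individual Part 1 samples on Days 30-31 could read 39-69% of a true trough at the stated terminal half-life. In a pooled arm mean, the fall is about 0.7-1.4% if 10% of Part 1 subjects are that late, or up to 2.1% on the accumulation-index sensitivity. The late-visit share is an assumption, and the 22% ceiling uses planned counts.

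A reader might infer that trough exposure is systematically understated. The documents do not support this, because off-day visits without a hold push the other way and the net direction is unknown. Nor do they support any effect on the primary dose-response analysis, which uses randomised dose and clinical or MRI events rather than concentrations. A population PK model built on actual dose and sample times could accommodate the irregular timing.

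**What to change.** 1. **Protocol 4.5.** Tie the hold to the morning of the actual Day 28 visit. State that Part 1 subjects seen after Day 28 take their Day 28 dose as usual.
2. **SAP 7.7.** Delete the Cmax, AUC(0-24) and C(24) summaries to match Protocol 8.4.4. If Day 28 C(24) is kept, include only pre-dose samples whose last recorded dose was on the previous calendar day, and list the rest with actual times. Protocol 4.7 requires dosing dates on the eCRF but does not mention clock times, so use an hour-based window only if dose times are recorded.

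The cost is two sentences in the protocol and one deletion or one rule in the SAP. If the rule is used, some Day 28 samples leave the summary table. The Part 1 wording helps only subjects still entering Part 1, since SAP 2.2 says the move to Part 2 has been decided; the hold wording and the SAP change serve Part 2 as well.
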